6.11.5 Other Efficacy Endpoints

6.11.6 Multiplicity

No multiplicity adjustment will be made on the secondary and other efficacy endpoints.

6.12 Safety Analyses

The safety analyses will be presented by the treatment received for the Safety Population.

6.12.1 Adverse Events

Adverse events will be collected from the time of study drug administration through the last day of the subject's participation in the study.

A treatment emergent adverse event (TEAE) is defined as:

- Any AE that has an onset on or after the first dose of study drug, through the last day of the subject's participation in the study
- Any pre-existing AE that has worsened in severity on or after the first dose of study drug, through the last day of the subject's participation in the study

A treatment-related AE is defined as an AE classified by the Investigator as 'Related' to the study drug. If an AE has missing relationship it is assumed to be related to the study drug for analysis purposes.

Maximum severity (Life threatening) will be assumed for an AE with missing severity.

An overall summary table of AE incidence (number and percent of subjects) and number of events, will be presented by treatment group and overall, for the following categories:

- Any TEAE
- Treatment-Related TEAEs
- Serious TEAEs

- Serious Treatment-Related TEAEs
- TEAEs Leading to Study Drug Discontinuation
- TEAEs Leading to Early Withdrawal
- TEAEs Leading to Death

Summaries of TEAE incidence and number of events by SOC and PT will be presented by treatment group and overall, for the following:

- TEAEs
- Treatment-related TEAEs
- Serious TEAEs
- Serious Treatment-Related TEAEs
- TEAEs Leading to Study Drug Discontinuation
- TEAEs by Maximum Severity, (incidence only)
- Treatment-Related TEAEs by Maximum Severity, (incidence only)

The following listings of AEs will be presented in Section 14.3.2 of the CSR:

- Serious AEs
- AEs Leading to Early Withdrawal
- AEs Leading to Death

AE tabulations will be presented by SOC and PT in descending overall frequency of AE incidence and then alphabetically for ties.

All reported AEs will be listed in Appendix 16.2.7 of the CSR.

6.12.2 Laboratory Data

Descriptive statistics for the observed values and change from baseline will be presented by treatment group and visit for each hematology, urinalysis, and serum chemistry (including triglycerides and thyroid panel) parameter. Each continuous measurement will be classified as below, within, or above normal range, based on ranges supplied by the laboratory used. Categorical parameters may also be classified as normal or abnormal based on normal ranges, and subject counts within each category will be summarized. Shift tables in relation to the normal range from baseline to each post-baseline visit will be presented.

Summaries and listings will be presented using the original unit for each parameter as received from the analytical laboratory.

A listing of out of normal range laboratory values throughout the study will be presented. All laboratory assessments, including urine pregnancy tests, drug tests, and serology will also be listed.

A separate listing will be provided for all Alanine Aminotransferase (ALT), Aspartate Aminotransferase (AST), and Bilirubin results at all timepoints for any subjects who meet the criteria for liver function abnormalities as defined in Section 0.

6.12.3 Vital Signs

Descriptive statistics for observed values and changes from baseline in the following vital signs will be tabulated at each post-baseline visit:

- Systolic blood pressure (mmHg)
- Diastolic blood pressure (mmHg)
- Pulse rate (bpm)
- Body weight (kg)

All vital signs measurements throughout the study will be listed.

6.12.4 Electrocardiogram Data

Descriptive statistics for observed values and changes from baseline in the following ECG variables will be tabulated at each post-baseline visit:

- Heart rate (bpm)
- PR interval (ms)
- RR interval (ms)
- QRS complex (ms)
- QT interval (ms)
- QTc interval (ms) [Bazett's formula - QTcB]
- QTc interval (ms) [Fridericia's formula - QTcF]

Shift tables in relation to the overall interpretation (Normal, Abnormal Not Clinically Significant [NCS], and Abnormal Clinically Significant [CS]) from baseline to each post-baseline visit will be presented.

All ECG assessments throughout the study will be listed.

6.12.5 Sheehan-Suicidality Tracking Scale

Descriptive statistics for observed and change from baseline S-STS total score will be summarized by treatment group for each post-baseline visit.

All S-STS responses throughout the study will be listed.

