12.7.5. Suicidal Ideation

Subjects with suicidal ideation or behavior will be identified with the S-STS.

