3.3 Other Efficacy Endpoints

3.4 Safety Endpoints

The safety endpoints will include adverse events (AE), serious adverse events (SAE), discontinuation due to adverse events and the S-STS. Vital signs, physical examination, electrocardiogram and standard clinical laboratory parameters will also be assessed.

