4 SAMPLE SIZE

The planned sample size is a total of 300 randomized subjects with 100 subjects per treatment group. Efficacy analyses will include all subjects who receive at least one dose of study drug and who have at least one post baseline assessment. It is expected that approximately 15% of subjects will be excluded from the efficacy population. A total of 85 subjects per treatment arm will provide approximately 88% power to detect a difference in means of 0.73 for NYX-2925 50 mg or 100 mg versus Placebo group assuming that the common standard deviation is 1.7 without correcting for multiple testing, using one-sided statistical testing with an overall Type I error rate of 0.05.

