6.3.4 Descriptive Statistics

Continuous variables will be summarized by the number of non-missing observations, mean, median, standard deviation, and minimum and maximum.

Categorical variables will be summarized by presenting the frequency and percent. Percentages will be based on the number of non-missing observations or the subject population unless

otherwise specified. For each variable, all categories will be shown. Zero frequencies (but not the percent) within a category will be presented.

Incidences of adverse events, medical history and concomitant medications will be reported at the subject level. Subjects can only be counted once within each PT and SOC under the highest severity and most related. Percentages will be calculated using the number of subjects in the treatment group for the Safety Population.

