16.2.6.1	Average Pain Intensity Related to Fibromyalgia in The Past 24 Hours - Weekly Mean NRS Score - Modified Intent-to-Treat Population	IP	
16.2.6.2	Daily Rescue Medication Usage - Modified Intent-to-Treat Population	IP	
16.2.6.3	Daily Sleep Interference Scale - Modified Intent-to-Treat Population	IP	
16.2.6.4	Fibromyalgia Impact Questionnaire – Revised Score - Modified Intent-to-Treat Population	IP	

16.2.6.5	Patient Reported Outcomes Measurement Information System Sleep Disturbance Score - Modified Intent-to-Treat Population	IP	
16.2.6.6	Patient Reported Outcomes Measurement Information System – Fibromyalgia Fatigue Profile Score - Modified Intent-to-Treat Population	IP	
16.2.6.7	Patient Reported Outcomes Measurement Information System Physical Function Score - Modified Intent-to-Treat Population	IP	
16.2.6.8	Patient Global Impression of Severity - Modified Intent-to-Treat Population	IP	
16.2.6.9	Patient Global Impression of Change - Modified Intent-to-Treat Population	IP	
16.2.6.10	Hospital Anxiety and Depression Scale – Modified Intent-to-Treat Population		
16.2.6.11	Sheehan-Suicidality Tracking Scale - Modified Intent-to-Treat Population	IP	
16.2.6.12	Time to First $\geq 30\%$ or $\geq 50\%$ Reduction in Mean NRS Score for Average Pain Intensity Related to Fibromyalgia – Modified Intent-to-Treat Population	IP	
16.2.7	Adverse Event Listings	IP	
16.2.7.1	Adverse Event Data - Safety Population	IP	
16.2.8	Individual Laboratory Measurements and Other Safety	IP	
16.2.8.1	Hematology Data - Safety Population	IP	
16.2.8.2	Serum Chemistry Data - Safety Population	IP	
16.2.8.3	Urinalysis Data - Safety Population	IP	
16.2.8.4	Thyroid Panel Data - Safety Population	IP	
16.2.8.5	Serology Data - Safety Population	IP	
16.2.8.6	Vital Signs Data - Safety Population	IP	
16.2.8.7	Electrocardiogram Data - Safety Population	IP	
16.2.8.8	Physical Examination Data - Safety Population	IP	
16.2.8.9	Neurological Examination Data - Safety Population	IP	
16.2.8.10	Urine Pregnancy Testing Data - Safety Population	IP	
16.2.8.11	Urine Drug Screening Data - Safety Population	IP	

Study Name: A Randomized, Double-Blind, Placebo-Controlled Study to Assess the Efficacy and Safety of NYX-2925 in Subjects with Fibromyalgia

Statistical Analysis Plan (SAP)
Version being approved: NYX-2925-2005_SAP_V1.0, dated 21July2022

Tables, Figures and Listings
(TFL) Shell version being
approved: NYX-2925-2005_TFL_Shells_V1.0, dated 21July2022

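### The S-STS safety endpoint is summarised only as a continuous total score, with no count of affected subjects by arm, and its only response listing is limited to the mITT population

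*SAP*

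**What the plan says.** **Status of the scale.** SAP 3.4 states: "The safety endpoints will include adverse events (AE), serious adverse events (SAE), discontinuation due to adverse events and the S-STS". Protocol 5.3.3 names the same endpoints. Protocol 12.7.5 gives its purpose at subject level: "Subjects with suicidal ideation or behavior will be identified with the S-STS". The scale is completed at screening, baseline, Weeks 2, 4 and 8, and at Week 12 or early termination.

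**Planned summary.** SAP 6.12.5: "Descriptive statistics for observed and change from baseline S-STS total score will be summarized by treatment group", at each visit after baseline. SAP 6.3.4 fixes the statistics: "Continuous variables will be summarized by the number of non-missing observations, mean, median, standard deviation, and minimum and maximum". The index has one S-STS table, 14.3.7.7, on the Safety Population.

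**Planned listing.** SAP 6.12.5: "All S-STS responses throughout the study will be listed". The index has one S-STS listing, 16.2.6.11, titled "Sheehan-Suicidality Tracking Scale - Modified Intent-to-Treat Population" and filed under the heading for individual efficacy data. SAP 6.12 puts safety analyses on the Safety Population.

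**Populations.** The Safety Population is every subject with at least one dose (SAP 6.1.3). The mITT Population is the part of it with at least one pain NRS assessment after baseline (SAP 6.1.4).

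**Adverse-event route.** Protocol 9.3.6 has suicidality found after baseline recorded as an adverse event. SAP 6.12.1 tabulates treatment-emergent events by system organ class and preferred term, and Listing 16.2.7.1 shows all adverse events for the Safety Population.

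**Not visible.** Part of SAP 6.2.24, which describes the S-STS, is redacted. The post-lock addendum does not change 6.12.5 or the S-STS outputs.

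**The concern.** The safety question is how many subjects in each arm had suicidal ideation or behaviour after starting treatment. That is a count of uncommon events. The planned table answers a different question: how the distribution of a total score moves at each visit. The protocol's subject-level purpose therefore has no tabulated output.

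The listing is where a reader would go to recover the cases one by one. Its population is set by whether a subject gave a pain score after baseline, which has no bearing on suicidality. If the label is programmed as written, the table and the listing that should support it will cover different sets of subjects and may not reconcile. The laboratory, ECG, vital-sign and adverse-event listings are all on the Safety Population, so the S-STS is the exception among the safety measures.

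**Working it through.** The plan states no figure to reproduce on this point. The check compares the relevant sections and adds one small illustration.

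**Step 1. Is there any count?** I looked for a categorical S-STS output in SAP 6.12.5 and in the table, figure and listing index. There is one table (continuous) and one listing. Other safety domains do get categorical output: shift tables for laboratory values (6.12.2) and for ECG interpretation (6.12.4). The S-STS gets none.

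**Step 2. Could the planned statistics stand in for a count?** Inputs: 100 subjects per arm (SAP 4). The score changes below are assumptions for illustration, since the documents give no S-STS change. The shift in the arm mean is k × d / n for k subjects each rising d points in an arm of n.

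| Rise d | k = 1 | k = 3 |
|---|---|---|
| 4 | 1 × 4 / 100 = 0.04 | 3 × 4 / 100 = 0.12 |
| 10 | 1 × 10 / 100 = 0.10 | 3 × 10 / 100 = 0.30 |
| 20 | 1 × 20 / 100 = 0.20 | 3 × 20 / 100 = 0.60 |

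The mean alone says little, but the plan also reports the median, SD, minimum and maximum. Take two arms of 100:

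- Arm A: one subject +10, ten subjects −1, 89 unchanged. Sum = 10 − 10 = 0. Mean 0, median 0, minimum −1, maximum 10. SD = √((100 + 10) / 99) = 1.05.
- Arm B: one subject +10, three subjects +4, 22 subjects −1, 74 unchanged. Sum = 10 + 12 − 22 = 0. Mean 0, median 0, minimum −1, maximum 10. SD = √((100 + 48 + 22) / 99) = 1.31.

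The n, mean, median, minimum and maximum are identical, and the SD differs only moderately. One subject worsened in arm A and four in arm B. The maximum shows the largest rise in each arm at each visit, but not how many subjects rose. Because the table is by visit, it also cannot show how many different subjects were affected at any time. Nor can a total separate ideation from behaviour, assuming the total adds the items (its definition is partly redacted).

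**Step 3. Who would be in the table but not in the listing?** Three conditions must hold together:

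1. the subject took at least one dose (in the Safety Population);
2. no pain NRS was recorded after baseline (outside mITT);
3. an S-STS was completed after baseline.

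The third is possible. The early termination visit includes the S-STS (Protocol 10.3.3), and SAP 6.2.11 maps an early-withdrawal S-STS on Day 2 to Day 21 to Week 2. Such a subject contributes to Table 14.3.7.7 and is absent from Listing 16.2.6.11. For a dosed subject who meets only the first two conditions, the screening and baseline responses are still missing from the listing, although 6.12.5 says every response in the study will be listed.

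**Step 4. How many?** The documents give no number. The diary is completed every night, and a single entry after baseline places a dosed subject in mITT. The group meeting all three conditions is therefore probably small.

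**Step 5. What does the adverse-event route cover?** It covers the Safety Population and every case a site records as an adverse event. It plans no grouped suicidality summary, so related events may be spread over several preferred terms. It also depends on the site turning a scale answer into an adverse event, including at Week 2, when the form is completed on paper during a remote visit and returned later. SAP 6.12.6 repeats the record-as-an-adverse-event rule for misuse and abuse events; SAP 6.12.5 does not repeat it for the S-STS.

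**The case against.** The other side has four fair arguments.

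- **The protocol promises identification, not a count, and a listing identifies.** This stands as far as it goes: a count table is a sensible addition, not a broken promise. But a listing restricted to mITT does not identify everyone, and reading a listing is not a comparison by arm.
- **The maximum will reveal a large rise.** True when that rise is the largest in its arm and visit. It does not say how many subjects were affected.
- **Suicidality must be recorded as an adverse event, and adverse events are fully tabulated and listed.** This is the strongest argument and it largely stands. A count taken from the scale would complement that route and check it.
- **The redacted text in SAP 6.2.24 may define S-STS categories.** It may, and this limits confidence. No categorical output appears in 6.12.5 or in the index.

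A reader might also draw stronger conclusions that the documents do not support.

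- *Only mean change is reported, so cases are averaged away.* Observed scores are summarised too, with median, SD, minimum and maximum.
- *S-STS reporting as a whole is confined to the efficacy population.* The summary table is on the Safety Population; only the listing is not.
- *A sizeable share of subjects is missing from the listing.* SAP 4 expects that "approximately 15% of subjects will be excluded from the efficacy population", and 0.15 × 300 = 45. That is a planning allowance on randomised subjects. It may include subjects never dosed, and it does not require a post-baseline S-STS, so it does not measure the group in question.
- *Early leavers are the ones omitted.* An early leaver with a single diary entry after baseline is in mITT and in the listing.

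**Conclusion.** The point holds as two limited gaps. First, the visible plan has no by-arm count of subjects with post-baseline ideation or behaviour on a named safety endpoint, and the planned total-score statistics cannot supply one. Second, the population label on Listing 16.2.6.11 contradicts SAP 6.12.5 and 6.12.

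The size is modest. One descriptive table is missing and one label is wrong. The number of subjects affected by the label is not given and is probably small. Cases are not wholly lost, since the adverse-event tables and listing cover the Safety Population. What is missing is a count from the scale itself and, for dosed subjects outside mITT, the individual S-STS responses.

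This rests on two assumptions: that the redacted part of SAP 6.2.24 does not lead to a categorical output absent from the index, and that the listing would be programmed on the population in its title. The score changes in the working are illustrative and carry no weight in the conclusion.

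**What to change.** Add to SAP 6.12.5 and the index one descriptive table on the Safety Population: the number and percent of subjects in each arm with any S-STS ideation or behaviour after baseline. Define the two categories from the scale's own items, or from SAP 6.2.24 if the redacted text already does so, and document the definition before the table is run. Relabel Listing 16.2.6.11 to the Safety Population, so that it matches 6.12.5 and reconciles with Table 14.3.7.7.

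The cost is one table and one population label. No new data and no hypothesis test are needed. The SAP already has an addendum written after unblinding, so the table would now enter as an additional report output, which SAP 6 allows if the justification is documented. Because it is descriptive, it does not affect any error rate.

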6.12.6 Misuse, Abuse, and Diversion Drug Event Reporting System

Potentially aberrant drug behavior (i.e., misuse and abuse-related events) will be identified, assessed, and quantified using the Misuse, Abuse, and Diversion Drug Event Reporting System (MADDERS[®]), which consists of a set of forms completed by Investigators or qualified Sub-investigators when potential abuse-related events are identified and upon the completion of each subject's participation in the study. Any misuse and abuse-related event will be recorded as an adverse event. A separate independent report will be provided by the data vendor for inclusion in the CSR.

7 INTERIM ANALYSIS

No interim analyses are planned.

8 DATA SAFETY MONITORING BOARD ANALYSIS

No data safety monitoring board (DSMB) analyses are planned.

9 CHANGES TO PLANNED PROTOCOL ANALYSIS

- Changing analyses of efficacy from 2-sided testing to 1-sided testing.
- The Patient Reported Outcomes Measurement Information System – Fibromyalgia (PROMIS_{FM}) physical function score is updated to Patient Reported Outcomes Measurement Information System (PROMIS) physical function score, and Patient Reported Outcomes Measurement Information System – Fibromyalgia (PROMIS_{FM}) sleep disturbance score is updated to Patient Reported Outcomes Measurement Information System (PROMIS) sleep disturbance score.
- Changing the primary efficacy endpoint from ‘change from baseline in the weekly mean of the daily Numerical Rating Scale (NRS) score assessing average pain intensity related to fibromyalgia in the past 24 hours’ to ‘change from baseline to Week 12 in the weekly

mean of the daily Numerical Rating Scale (NRS) score assessing average pain intensity related to fibromyalgia in the past 24 hours'.

- [REDACTED]

11 LIST OF TABLES, FIGURES AND LISTINGS

The following table includes details of the tables, figures and listings to be included within each section of the eCTD. The eCTD section is shown in bold. The following validation methods maybe used

- Independent programming of numbers and manual review of format (IP)
- Independent programming by statistician of numbers and manual review of format (Stat IP)
- Manual review (MR)
- Code review (CR)

Table Number	Table Title	Validation Method	Shell Number (If Repeat)
14.1	Demographics Data		
14.1.1	Disposition		
14.1.1.1	Subject Disposition, Early Withdrawals - Screened Population	IP	
14.1.1.2	Subject Disposition, Screen Failures - Screened Population	IP	
14.1.1.3	Protocol Deviations - Safety Population	IP	
14.1.1.4	Populations by Center - Randomized Subjects	IP	
14.1.2	Demographics		
14.1.2.1	Demographics - Safety Population	IP	
14.1.3	Baseline Characteristics		
14.1.3.1	Medical History Prior to Screening by System Organ Class and Preferred Term - Safety Population	IP	
14.1.3.2	Medical History Ongoing at Screening by System Organ Class and Preferred Term - Safety Population	IP	14.1.3.1
14.1.3.3	Prior Medications by ATC Level 3 and Preferred Name - Safety Population	IP	
14.1.3.4	Ongoing Medications by ATC Level 3 and Preferred Name - Safety Population	IP	14.1.4.1
14.1.3.5	Patient Global Impression of Severity at Baseline - Safety Population	IP	
14.1.3.6	Physical Examination at Baseline - Safety Population	IP	
14.1.3.7	Neurological Examination at Baseline - Safety Population	IP	
14.2	Efficacy Analysis – 1-Sided Test		
14.2.1	Primary Efficacy Endpoint		

14.2.1.1.1	Primary Endpoint: Change from Baseline to until Week 12 in Weekly Mean NRS Score, Mixed Model for Repeated Measures – 1-Sided Test - Modified Intent-to-Treat Population	Stat IP	
14.2.1.1.2	Primary Endpoint: Change from Baseline to until Week 12 in Weekly Mean NRS Score, Mixed Model for Repeated Measures – 2-Sided Test - Modified Intent-to-Treat Population	Stat IP	14.2.1.1.1
14.2.1.2.1	Sensitivity Analysis (1): Change from Baseline to until Week 12 in Weekly Mean NRS Score, Pattern-Mixture Model – 1-Sided Test - Modified Intent-to-Treat Population	Stat IP	
14.2.1.2.2	Sensitivity Analysis (1): Change from Baseline to until Week 12 in Weekly Mean NRS Score, Pattern-Mixture Model – 2-Sided Test - Modified Intent-to-Treat Population	Stat IP	14.2.1.2.1
14.2.1.3.1	Sensitivity Analysis (2): Change from Baseline in Weekly Mean NRS score at Week 12, Tipping Point Analysis – 1-Sided Test - Modified Intent-to-Treat Population	Stat IP	
14.2.1.3.2	Sensitivity Analysis (2): Change from Baseline in Weekly Mean NRS score at Week 12, Tipping Point Analysis – 2-Sided Test - Modified Intent-to-Treat Population	Stat IP	14.2.1.3.1
14.2.1.4.1	Supportive Analysis: Change from Baseline in Weekly Mean NRS Score at Week 12, Analysis of Covariance – 1-Sided Test - Modified Intent-to-Treat Population	Stat IP	
14.2.1.4.2	Supportive Analysis: Change from Baseline in Weekly Mean NRS Score at Week 12, Analysis of Covariance – 2-Sided Test - Modified Intent-to-Treat Population	Stat IP	14.2.1.4.1
14.2.1.5.1	Pooled Analysis: Change from Baseline to until Week 12 in Weekly Mean NRS Score, Mixed Model for Repeated Measures – 1-Sided Test - Modified Intent-to-Treat Population	Stat IP	
14.2.1.5.2	Pooled Analysis: Change from Baseline to until Week 12 in Weekly Mean NRS Score, Mixed Model for Repeated Measures – 2-Sided Test - Modified Intent-to-Treat Population	Stat IP	14.2.1.5.1
14.2.1.6.1	Exploratory Analysis: Change from Baseline to until Week 12 in Weekly Mean NRS Score, By Baseline NRS Score, Mixed Model for Repeated Measures - 1-Sided Test - Modified Intent-to-Treat Population	Stat IP	14.2.1.1.1
14.2.1.6.2	Exploratory Analysis: Change from Baseline to until Week 12 in Weekly Mean NRS Score, By Baseline NRS Score, Mixed Model for Repeated Measures - 2-Sided Test - Modified Intent-to-Treat Population	Stat IP	14.2.1.1.1

14.2.1.7.1	Exploratory Analysis: Change from Baseline to until Week 12 in Weekly Mean NRS Score, By Baseline DSIS Score, Mixed Model for Repeated Measures – 1-Sided Test - Modified Intent-to-Treat Population	Stat IP	14.2.1.1.1
14.2.1.7.2	Exploratory Analysis: Change from Baseline to until Week 12 in Weekly Mean NRS Score, By Baseline DSIS Score, Mixed Model for Repeated Measures – 2-Sided Test - Modified Intent-to-Treat Population	Stat IP	14.2.1.1.1
14.2.1.8.1	Exploratory Analysis: Change from Baseline to until Week 12 in Weekly Mean NRS Score, By Baseline PROMIS _{FM} Fatigue Profile Score, Mixed Model for Repeated Measures – 1-Sided Test - Modified Intent-to-Treat Population	Stat IP	14.2.1.1.1
14.2.1.8.2	Exploratory Analysis: Change from Baseline to until Week 12 in Weekly Mean NRS Score, By Baseline PROMIS _{FM} Fatigue Profile Score, Mixed Model for Repeated Measures – 2-Sided Test - Modified Intent-to-Treat Population	Stat IP	14.2.1.1.1
14.2.1.9.1	Exploratory Analysis: Change from Baseline to until Week 12 in Weekly Mean NRS Score, By Baseline PROMIS Physical Function Score, Mixed Model for Repeated Measures – 1-Sided Test - Modified Intent-to-Treat Population	Stat IP	14.2.1.1.1
14.2.1.9.2	Exploratory Analysis: Change from Baseline to until Week 12 in Weekly Mean NRS Score, By Baseline PROMIS Physical Function Score, Mixed Model for Repeated Measures – 2-Sided Test - Modified Intent-to-Treat Population	Stat IP	14.2.1.1.1
14.2.1.10.1	Exploratory Analysis: Change from Baseline to until Week 12 in Weekly Mean NRS Score, By Baseline PROMIS Sleep Disturbance Score, Mixed Model for Repeated Measures – 1-Sided Test - Modified Intent-to-Treat Population	Stat IP	14.2.1.1.1
14.2.1.10.2	Exploratory Analysis: Change from Baseline to until Week 12 in Weekly Mean NRS Score, By Baseline PROMIS Sleep Disturbance Score, Mixed Model for Repeated Measures – 2-Sided Test - Modified Intent-to-Treat Population	Stat IP	14.2.1.1.1
14.2.1.11.1	Exploratory Analysis: Change from Baseline to until Week 12 in Weekly Mean NRS Score, By Baseline HADS Depression Subscale, Mixed Model for Repeated Measures – 1-Sided Test - Modified Intent-to-Treat Population	Stat IP	14.2.1.1.1
14.2.1.11.2	Exploratory Analysis: Change from Baseline to until Week 12 in Weekly Mean NRS Score, By Baseline HADS Depression Subscale, Mixed Model for Repeated Measures – 2-Sided Test - Modified Intent-to-Treat Population	Stat IP	14.2.1.1.1

14.2.1.12.1	Exploratory Analysis: Change from Baseline to until Week 12 in Weekly Mean NRS Score, By Baseline HADS Anxiety Subscale, Mixed Model for Repeated Measures – 1-Sided Test - Modified Intent-to-Treat Population	Stat IP	14.2.1.1.1
14.2.1.12.2	Exploratory Analysis: Change from Baseline to until Week 12 in Weekly Mean NRS Score, By Baseline HADS Anxiety Subscale, Mixed Model for Repeated Measures – 2-Sided Test - Modified Intent-to-Treat Population	Stat IP	14.2.1.1.1
14.2.1.13.1	Subgroup Analysis: Change from Baseline to until Week 12 in Weekly Mean NRS Score, By Baseline NRS Score, Mixed Model for Repeated Measures – 1-Sided Test - Modified Intent-to-Treat Population	Stat IP	14.2.1.1.1
14.2.1.13.2	Subgroup Analysis: Change from Baseline to until Week 12 in Weekly Mean NRS Score, By Baseline NRS Score, Mixed Model for Repeated Measures – 2-Sided Test - Modified Intent-to-Treat Population	Stat IP	14.2.1.1.1
14.2.1.14.1	Subgroup Analysis: Change from Baseline to until Week 12 in Weekly Mean NRS Score, By Prior Analgesic Use, Mixed Model for Repeated Measures – 1-Sided Test - Modified Intent-to-Treat Population	Stat IP	14.2.1.1.1
14.2.1.14.2	Subgroup Analysis: Change from Baseline to until Week 12 in Weekly Mean NRS Score, By Prior Analgesic Use, Mixed Model for Repeated Measures – 2-Sided Test - Modified Intent-to-Treat Population	Stat IP	14.2.1.1.1
14.2.1.15.1	Subgroup Analysis: Change from Baseline to until Week 12 in Weekly Mean NRS Score, By Subject Sourced via AES, Mixed Model for Repeated Measures – 1-Sided Test - Modified Intent-to-Treat Population	Stat IP	14.2.1.1.1
14.2.1.15.2	Subgroup Analysis: Change from Baseline to until Week 12 in Weekly Mean NRS Score, By Subject Sourced via AES, Mixed Model for Repeated Measures – 2-Sided Test - Modified Intent-to-Treat Population	Stat IP	14.2.1.1.1
14.2.1.16.1	Subgroup Analysis: Change from Baseline to until Week 12 in Weekly Mean NRS Score, By Sourced via AES and with Baseline NRS Score ≥ 5.0 versus Otherwise, Mixed Model for Repeated Measures – 1-Sided Test – Modified Intent-to-Treat Population	Stat IP	14.2.1.1.1
14.2.1.16.2	Subgroup Analysis: Change from Baseline to until Week 12 in Weekly Mean NRS Score, By Sourced via AES and with Baseline NRS Score ≥ 5.0 versus Otherwise, Mixed Model for Repeated Measures – 2-Sided Test – Modified Intent-to-Treat Population	Stat IP	14.2.1.1.1

14.2.1.17.1	Subgroup Analysis: Change from Baseline to until Week 12 in Weekly Mean NRS Score, By Time since Diagnosed Fibromyalgia \geq Mean versus Otherwise, Mixed Model for Repeated Measures – 1-Sided Test – Modified Intent-to-Treat Population	Stat IP	14.2.1.1.1
14.2.1.17.2	Subgroup Analysis: Change from Baseline to until Week 12 in Weekly Mean NRS Score, By Time since Diagnosed Fibromyalgia \geq Mean versus Otherwise, Mixed Model for Repeated Measures –2-Sided Test – Modified Intent-to-Treat Population	Stat IP	14.2.1.1.1
14.2.2	Secondary Efficacy Endpoints		
14.2.2.1.1	Patient Global Impression of Change, Percentage of Subjects ‘Much Improved’ or ‘Very Much Improved’ by Visit, Chi-Square Test – 1-Sided Test - Modified Intent-to-Treat Population	IP	
14.2.2.1.2	Patient Global Impression of Change, Percentage of Subjects ‘Much Improved’ or ‘Very Much Improved’ by Visit, Chi-Square Test – 2-Sided Test - Modified Intent-to-Treat Population	IP	14.2.2.1.1
14.2.2.2.1	Patient Global Impression of Change, Change from Baseline to until Week 12, Mixed Model for Repeated Measures –1-Sided Test – Modified Intent-to-Treat Population	Stat IP	14.2.1.1.1
14.2.2.2.2	Patient Global Impression of Change, Change from Baseline to until Week 12, Mixed Model for Repeated Measures –2-Sided Test – Modified Intent-to-Treat Population	Stat IP	14.2.1.1.1
14.2.2.3.1	Daily Sleep Interference Scale, Change from Baseline to until Week 12 in Weekly Mean Score, Mixed Model for Repeated Measures –1-Sided Test – Modified Intent-to-Treat Population	Stat IP	14.2.1.1.1
14.2.2.3.2	Daily Sleep Interference Scale, Change from Baseline to until Week 12 in Weekly Mean Score, Mixed Model for Repeated Measures –2-Sided Test – Modified Intent-to-Treat Population	Stat IP	14.2.1.1.1
14.2.2.4.1	Percentage of Subjects Achieving \geq 30% Reduction or \geq 50% Reduction in Weekly Mean NRS Score at Week 12, Chi-Square Test – 1-Sided Test – Modified Intent-to-Treat Population	IP	
14.2.2.4.2	Percentage of Subjects Achieving \geq 30% Reduction or \geq 50% Reduction in Weekly Mean NRS Score at Week 12, Chi-Square Test – 2-Sided Test – Modified Intent-to-Treat Population	IP	14.2.2.4.1
14.2.2.5.1	Fibromyalgia Impact Questionnaire – Revised (FIQR) Scores, Change from Baseline to until Week 12, Mixed model for Repeated Measures – 1-Sided Test – Modified Intent-to-Treat Population	Stat IP	

14.2.2.5.2	Fibromyalgia Impact Questionnaire – Revised (FIQR) Scores, Change from Baseline to until Week 12, Mixed model for Repeated Measures – 2-Sided Test – Modified Intent-to-Treat Population	Stat IP	14.2.2.5.1
14.2.2.6.1	Patient Reported Outcome Measurement Information System – Fibromyalgia (PROMIS _{FM}) Fatigue Profile Score, Change from Baseline to until Week 12, Mixed model for Repeated Measures – 1-Sided Test – Modified Intent-to-Treat Population	Stat IP	
14.2.2.6.2	Patient Reported Outcome Measurement Information System – Fibromyalgia (PROMIS _{FM}) Fatigue Profile Score, Change from Baseline to until Week 12, Mixed model for Repeated Measures – 2-Sided Test – Modified Intent-to-Treat Population	Stat IP	
14.2.2.7.1	Patient Reported Outcome Measurement Information System (PROMIS) Sleep Disturbance Score, Change from Baseline to until Week 12, Mixed model for Repeated Measures – 1-Sided Test – Modified Intent-to-Treat Population	Stat IP	14.2.1.1.1
14.2.2.7.2	Patient Reported Outcome Measurement Information System (PROMIS) Sleep Disturbance Score, Change from Baseline to until Week 12, Mixed model for Repeated Measures – 2-Sided Test – Modified Intent-to-Treat Population	Stat IP	14.2.1.1.1
14.2.2.8.1	Patient Reported Outcome Measurement Information System (PROMIS) Physical Function Score, Change from Baseline to until Week 12, Mixed model for Repeated Measures – 1-Sided Test – Modified Intent-to-Treat Population	Stat IP	14.2.1.1.1
14.2.2.8.2	Patient Reported Outcome Measurement Information System (PROMIS) Physical Function Score, Change from Baseline to until Week 12, Mixed model for Repeated Measures – 2-Sided Test – Modified Intent-to-Treat Population	Stat IP	14.2.1.1.11
14.2.2.9.1	Average Pain Intensity, Cumulative Response in Weekly Mean NRS Score at Week 12, Kolmogorov-Smirnov Test – 2-Sided Test – Modified Intent-to-Treat Population	IP	
14.2.2.9.2	Average Pain Intensity, Cumulative Response in Weekly Mean NRS Score at Week 12, Kolmogorov-Smirnov Test – 1-Sided Test – Modified Intent-to-Treat Population	IP	14.2.2.9.1
14.2.2.10	Rescue Medication, Total Number of Tablets Taken Per Week, Descriptive Statistics – Modified Intent-to-Treat Population	Stat IP	
14.2.2.11	Rescue Medication, Percentage of Rescue-Free Days Per Week, Descriptive Statistics – Modified Intent-to-Treat Population	Stat IP	
14.2.2.12.1	Proportion of Subjects Using Rescue Medication During the Study, Chi-Square Test – 1-Sided Test – Modified Intent-to-Treat Population	IP	

14.2.2.12.2	Proportion of Subjects Using Rescue Medication During the Study, Chi-Square Test – 2-Sided Test – Modified Intent-to-Treat Population	IP	14.2.2.12.1
14.2.2.13.1	Rescue Medication, Weekly Mean Dose Up to Week 12, Mixed Model for Repeated Measures – 1-Sided Test – Modified Intent-to-Treat Population	IP	14.2.1.1.1
14.2.2.13.2	Rescue Medication, Weekly Mean Dose Up to Week 12, Mixed Model for Repeated Measures – 2-Sided Test – Modified Intent-to-Treat Population	IP	14.2.1.1.1
14.2.3	Other Efficacy Endpoints	IP	
14.2.3.1.1	Time in Days to First $\geq 30\%$ Reduction in Weekly Mean NRS Score, Log-Rank Test – 1-Sided Test – Modified Intent-to-Treat Population	IP	
14.2.3.1.2	Time in Days to First $\geq 30\%$ Reduction in Weekly Mean NRS Score, Log-Rank Test – 2-Sided Test – Modified Intent-to-Treat Population	IP	14.2.3.1.1
14.2.3.2.1	Average Pain Intensity Related to Fibromyalgia, Time in Days to the First $\geq 50\%$ Reduction Weekly Mean NRS – 1-Sided Test – Modified Intent-to-Treat Population	IP	14.2.3.1.1
14.2.3.2.2	Average Pain Intensity Related to Fibromyalgia, Time in Days to the First $\geq 50\%$ Reduction Weekly Mean NRS – 2-Sided Test – Modified Intent-to-Treat Population	IP	14.2.3.1.1
14.2.3.3.1	Hospital Anxiety and Depression Scale (HADS), Change in Subscale Score from Baseline to until Week 12, Mixed model for Repeated Measures – 1-Sided Test – Modified Intent-to-Treat Population	IP	14.2.1.1.1
14.2.3.3.2	Hospital Anxiety and Depression Scale (HADS), Change in Subscale Score from Baseline to until Week 12, Mixed model for Repeated Measures – 2-Sided Test – Modified Intent-to-Treat Population	IP	14.2.1.1.1
14.2.3.4.1	Average Pain Intensity Related to Fibromyalgia, Percentage of Subjects Achieving $\geq 30\%$ Reduction or $\geq 50\%$ Reduction in Weekly Mean NRS Score from Baseline to until Week 12, Chi-Square Test – 1-Sided Test – Modified Intent-to-Treat Population	IP	14.2.2.3.1
14.2.3.4.2	Average Pain Intensity Related to Fibromyalgia, Percentage of Subjects Achieving $\geq 30\%$ Reduction or $\geq 50\%$ Reduction in Weekly Mean NRS Score from Baseline to until Week 12, Chi-Square Test – 2-Sided Test – Modified Intent-to-Treat Population	IP	14.2.2.3.1
14.3	Safety Data	IP	

14.3.1	Displays of Adverse Events	IP	
14.3.1.1	Overall Summary of Adverse Events – Safety Population	IP	
14.3.1.2	Treatment Emergent Adverse Events by System Organ Class and Preferred Term – Safety Population	IP	
14.3.1.3	Treatment Emergent Adverse Events Related to Study Drug by System Organ Class and Preferred Term – Safety Population	IP	14.3.1.2
14.3.1.4	Serious Treatment Emergent Adverse Events by System Organ Class and Preferred Term – Safety Population	IP	14.3.1.2
14.3.1.5	Serious Treatment Emergent Adverse Events Related to Study Drug by System Organ Class and Preferred Term – Safety Population	IP	14.3.1.2
14.3.1.6	Treatment Emergent Adverse Events Leading to Study Drug Discontinuation by System Organ Class and Preferred Term – Safety Population	IP	14.3.1.2
14.3.1.7	Treatment Emergent Adverse Events by System Organ Class, Preferred Term and Maximum Severity – Safety Population	IP	
14.3.1.8	Treatment Emergent Adverse Events Related to Study Drug by System Organ Class, Preferred Term and Maximum Severity – Safety Population	IP	14.3.1.7
14.3.2	Listings of Deaths, Other Serious and Significant Adverse Events	IP	
14.3.2.1	Serious Adverse Events, Listing – Safety Population	IP	
14.3.2.2	Adverse Events Leading to Early Withdrawal, Listing – Safety Population	IP	14.3.2.1
14.3.2.3	Adverse Events Leading to Death, Listing – Safety Population	IP	14.3.2.1
14.3.4	Abnormal Laboratory Values	IP	
14.3.4.1	Liver Function Abnormalities, Listing - Safety Population	IP	
14.3.5	Extent of Exposure, Dosage Information, and Compliance	IP	
14.3.5.1	Exposure to Study Drug – Safety Population	IP	
14.3.5.2	Compliance with Study Drug – Safety Population	IP	
14.3.6	Vital Signs and Physical Examination	IP	
14.3.6.1	Vital Signs, Descriptive Statistics – Safety Population	IP	
14.3.6.2	Electrocardiogram Results, Change from Baseline – Safety Population	IP	
14.3.6.3	Electrocardiogram Results, Shift in Overall Interpretation – Safety Population	IP	
14.3.7	Other Safety	IP	
14.3.7.1	Hematology Data, Descriptive Statistics – Safety Population	IP	

14.3.7.2	Hematology Data, Normal Range Shifts – Safety Population	IP	
14.3.7.3	Serum Chemistry Data, Descriptive Statistics – Safety Population	IP	14.3.7.1
14.3.7.4	Serum Chemistry Data, Normal Range Shifts – Safety Population	IP	14.3.7.2
14.3.7.5	Urinalysis Data, Descriptive Statistics – Safety Population	IP	
14.3.7.6	Urinalysis Data, Normal Range Shifts – Safety Population	IP	14.3.7.2
14.3.7.7	Sheehan-Suicidality Tracking Scale, Change from Baseline – Safety Population	IP	
14.3.7.8	Concomitants Medications by ATC Level 3 and Preferred Name – Safety Population	IP	

Figure Number	Figure Title	Validation Method	Shell Number (if repeat)
14.2.1.1	Average Pain Intensity Related to Fibromyalgia, Change from Baseline in Weekly Mean NRS Score, LS Mean (95% CI) –Line Plot – Modified Intent-to-Treat Population	MR	
14.2.1.2	Average Pain Intensity Related to Fibromyalgia, LS Mean Difference in Weekly Mean NRS Score at Week 12, 1-Sided Analyses – Forest Plot – Modified Intent-to-Treat Population	MR	
14.2.1.3	Average Pain Intensity Related to Fibromyalgia, Change from Baseline in Weekly Mean NRS Score, LS Mean (95% CI) –Pooled Analysis - Line Plot – Modified Intent-to-Treat Population	MR	14.2.1.1
